9.2 Patient Discontinuation

Patients may discontinue study treatment and sample collection at any time. The primary reason for discontinuation should be recorded. Reasons for discontinuation of a patient by the investigator include, but are not limited to, the following:

- Need for additional use of ketorolac or other NSAIDs over the outlined collection period
- Clinically significant deterioration of the patient's condition during the study
- Patient noncompliance
- Peritoneal port failure
- Development of intra-abdominal complication
- Development of infectious morbidity
- Acute blood loss
- Investigator determination that it is not in the patient's best interest to continue participation

9.3 Study Discontinuation

It is unlikely that the trial itself will require a premature termination. However, the trial will be stopped prematurely (prior to completion of accrual, protocol therapy, and follow-up) for safety reasons.

10.0 STUDY ASSESSMENTS

All samples from the peritoneal cavity will be retrieved by the PI ([name]) or co-PI's ([name] and [name]) gynecologic oncologists who are skilled in the access and management of newly placed intraperitoneal ports. The ports will ideally be accessed at the time of surgery and access maintained until completion of the study endpoint samples.

10.1 Pre-treatment Sample Collection

- Collection of ascites cells at the time of tumor debulking
- Collection of peritoneal fluid and cells by the PI ([name]) or the co-PI's ([name] and [name]) and blood prior to ketorolac administration.

10.2 Post-treatment Sample Collection

- Collection of peritoneal fluid after ketorolac administration will be done at select time-points after ketorolac administration (1 hour, 6 hours, and 24 hours) an additional 48 hour sample (after the initial dose) will be done in patients having elective multiple ketorolac dosing.
- Cells and effluent will be separated from fluid at the above select time-points (1 hour, 6 hours, 24 hours) and at 48 hours after the initial ketorolac dose in patients who receive elective multiple ketorolac dosing.

10.3 Pharmacokinetic Evaluation:

Blood and 10-20 ccs of peritoneal fluid will be retrieved at the following time-points. Serum will be isolated and peritoneal fluid will be isolated from cellular material via centrifugation.

Timepoint	Time after ketorolac
1	Predose
2	1 hour
3	6 hours
4	24 hours
5	48 hours*

* elective time-point for patients receiving clinically indicated multiple dosing of ketorolac

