8.0 STUDY MODALITY

8.1 Ketorolac tromethamine (Toradol® Roche Pharmaceuticals)

Formulation: Ketorolac is supplied in sterile single use 1mL vials of 15 mg/mL (**NDC 55390-480-01**) and 30 mg/mL, 1 mL single-dose vials of 30mg/mL (**NDC 55390-481-01**). Supplies are obtained by the University Hospital (University of New Mexico) and stored in the Pyxis until ordered by the treating physician.

Preparation: Ketorolac tromethamine for IV use is supplied in 1 mL vials of either 15mg or 30mg individual dose which requires no reconstitution.

Storage: Vials of ketorolac tromethamine are stored at room temperature protected from light in the carton until use.

Dosing: Ketorolac tromethine will be dosed according to FDA approved recommendations. For planned **single dose (IV)** based on clinical scenario:

- Patients < 65 years of age: One dose of 30 mg.
- Patients ≥ 65 years of age, renally impaired and/or less than 50 kg (110 lbs) of body weight: One dose of 15 mg.

For planned **Multiple-Dose Treatment (IV)** for indicated pain management

- Patients < 65 years of age: The recommended dose is 30 mg ketorolac tromethamine injection every 6 hours. The maximum daily dose for these populations should not exceed 120 mg.

- For patients \geq 65 years of age, renal impaired patients, and patients less than 50 kg (110 lbs): The recommended dose is 15 mg ketorolac tromethamine injection every 6 hours. The maximum daily dose for these populations should not exceed 60 mg.

Adverse Effects: Complications of treatment with ketorolac tromethamine, such as G.I. ulceration, bleeding and perforation, postoperative bleeding, acute renal failure, anaphylactic and anaphylactoid reactions and liver failure have been described. These NSAID-related complications can be serious in certain patients for whom ketorolac tromethamine is indicated, especially when the drug is used inappropriately.

In patients taking ketorolac tromethamine or other NSAIDs in clinical trials, the most frequently reported adverse experiences and frequency are shown in the table below:

	< 1%	1%-10%	>10%
cardiovascular	CHF, palpitation, pallor, tachycardia, syncope	hypertension	
dermatologic	Alopecia, urticaria, photosensitivity	Injection site pain, rashes, pruritis	

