9.0 TREATMENT PLAN

All patients will receive a single dose of IV ketorolac for pain management for the indication of post-operative pain control. The single dose will be considered the study dose for which all consenting eligible patients will receive. The dose of IV ketorolac will be determined per the recommendations in the package insert. Patients less than 65 years of age and in otherwise good health will receive a 30mg IV single dose. Patients 65 years of age or greater, or who have mild renal insufficiency or are of low weight (as per section 3.2) will receive a single 15 mg dose IV ketorolac. In patients who have a clinical pain response and have no contraindications to multi-dose (every 6 hours over 24 hours), additional doses will be given per physician discretion based on clinical indication. Patients receiving 24 hour dosing will be eligible for sample time points after 24 hour dosing.

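### In patients who go on to elective dosing every 6 hours, the second dose is nominally due when the 6 h samples are due and no draw order is set, so a 6 h value meant to reflect one dose can contain two

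*Combined protocol and SAP*

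**What the plan says.** Section 9.0 gives every patient one dose: "The single dose will be considered the study dose". It then provides that, for patients with a pain response and "no contraindications to multi-dose (every 6 hours over 24 hours), additional doses will be given per physician discretion based on clinical indication". Section 8.1 repeats the 6-hour interval for multiple dosing.

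Section 10.2 samples peritoneal fluid at "select time-points after ketorolac administration (1 hour, 6 hours, and 24 hours", and the table in section 10.3 applies the same times to blood. For multi-dose patients, "an additional 48 hour sample (after the initial dose) will be done in patients having elective multiple ketorolac dosing". Only that 48 h sample is tied to the initial dose; the wording for 1, 6 and 24 h does not name a dose.

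The only instruction to sample before dosing is in section 10.1 and covers the pre-treatment sample: fluid, cells "and blood prior to ketorolac administration". No section sets the order of draw and dose at 6 h, a sampling window, or the recording of actual times.

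Section 11.2.1 analyses the data by repeated-measures ANOVA with Tukey comparisons and has no term for the number of doses received. Section 9.2 lists a need for additional ketorolac during the collection period as a reason for discontinuation, whereas sections 9.0 and 10.2 keep multi-dose patients in and sample them further.

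**The concern.** The primary objective is the concentration of R- and S-ketorolac in the peritoneal cavity and the percent racemic mixture after IV administration, with a single dose defined as the study dose. The 6 h sample can show R and S separating after that dose, because S is cleared faster.

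If some multi-dose patients are sampled before their second dose and others after it, the 6 h column mixes one-dose and two-dose values. A fresh racemic dose raises the concentration and pulls percent R back toward 50%, which masks the separation and widens the spread. The same fluid values feed the trend analysis on peritoneal R-ketorolac in section 11.2.2. Blood responds at once and fluid later, so a fluid-to-serum comparison at 6 h would be distorted too.

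The target is only 7-10 complete sets, so one or two such samples count. They cannot be redrawn, and without recorded times they may not be identifiable.

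**Working it through.** **The plan's own figures.** The only sample-size statement is the recruitment funnel in section 11.2.1: 60 × (1 − 0.60) = 24, against 25 stated; 25 − 18 = 7 and 25 − 15 = 10, which matches the 7-10 target. The plan states no expected 6 h concentration or percent R, so there is none to reproduce.

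**Inputs from section 1.5.2.** Half-life 5 h (SD 1.7) for R and 2.5 h (SD 0.4) for S; volume about 13 L after complete distribution; linear kinetics. Assumed: an equal R/S split and equal volumes for the two enantiomers.

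**Check against Table 2, 30 mg every 6 h.** With 13 L, the average is 2.08 µg/mL against 2.17 stated and the trough 1.16 against 1.04. The peak agrees (6.99 against 6.85) only if the stated single-dose peak of 4.65 is multiplied by the model's accumulation factor of 1.502. The 13 L volume alone gives 30/13 = 2.31 just after a dose, so the model understates the first minutes.

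**Serum at 6 h after 30 mg.** Each enantiomer starts at 15 mg / 13 L = 1.154 µg/mL.

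- One dose: R = 1.154 × 2^(−6/5) = 0.502; S = 1.154 × 2^(−6/2.5) = 0.219. Total 0.721; percent R = 0.502/0.721 = 69.7%.
- Second dose just before the draw: R = 0.502 + 1.154 = 1.656; S = 0.219 + 1.154 = 1.373. Total 3.029, a ratio of 4.20; percent R 54.7%. The 1 h value after one dose is 53.5%.
- Second dose 60 minutes before the draw: ratio 3.61; percent R 58.0%.
- Half-lives moved by one SD, dose just before the draw: ratio 3.6 to 5.7; percent R falls by 3 to 22 points.

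The ratios are the same for 15 mg.

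**Peritoneal fluid at 6 h.** Section 1.5.2 calls the distribution unknown. I assume first-order equilibration with serum at rate ke and apply it to both doses. A dose given u hours earlier contributes, per unit initial serum level, ke × (e^(−ku) − e^(−ke·u)) / (ke − k), where k is the enantiomer's elimination rate. The table covers a second dose 5 to 60 minutes before the draw.

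| Assumed equilibration half-life | Percent R, one dose | Percent R, two doses | Total, ratio |
|---|---|---|---|
| 0.25 h | 68.5% | 56.7% to 61.5% | 1.61 to 3.43 |
| 1 h | 64.4% | 57.9% to 62.7% | 1.14 to 2.10 |
| 4 h | 59.9% | 57.5% to 59.5% | 1.04 to 1.42 |
| 6.5 h | 59.2% | 57.3% to 58.9% | 1.03 to 1.35 |

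The smallest fall in percent R is 59.2 − 58.9 = 0.3 points. The largest in the table is 68.5 − 56.7 = 11.8; a finer grid over the same ranges peaks at 11.9. Every case raises concentration and moves percent R toward 50%.

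**Effect on a small set (serum, illustration).** If 2 of 7 patients were drawn just after a second dose, mean percent R is (5 × 69.7 + 2 × 54.7)/7 = 65.4%, and mean concentration is (5 + 2 × 4.20)/7 = 1.91 times the one-dose value.

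**The case against.** The strongest reply is that the effect on the primary measure may be small. Fluid is the primary matrix, its transfer rate is unknown, and with slow transfer and a dose given minutes before the draw the shift is 3-4% in concentration and under half a point in percent R. That stands. A reader might carry the 4.2-fold serum figure over to the fluid, but that needs instant equilibration, which the documents do not claim. A reader might instead delay only the second dose, adding 25-50% of it to an undelayed first dose; this gives 1.8 to 2.6-fold. It is inconsistent, because slow transfer delays the first dose as well.

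Three further limits stand. Added doses depend on pain response, contraindications and physician discretion, so the coincidence is nominal and the number of patients unstated. The stated pre-versus-post contrast is not threatened, since drug should be absent before dosing. And leaving out late-drawn samples costs data: one or two of seven is 14-29% of that time point.

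A reader might also infer that 6 h is the only sample after 1 h at which both enantiomers can be measured well. On these figures that is so after one dose: at 24 h, R is about 0.04 and S about 0.0015 µg/mL, against a lowest standard of 0.025 in section 10.3.1. It is not so in the patients at issue. With doses at 0, 6, 12 and 18 h, R is about 0.86 and S about 0.27 µg/mL at 24 h.

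Finally, section 9.2 might be read as removing multi-dose patients altogether. Sections 9.0 and 10.2 plainly keep them, so this is a contradiction to be reconciled, and none of the three sections settles the order at 6 h.

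**Conclusion.** The gap is real and confined to patients who continue on elective dosing. For them a 6 h value labelled as single-dose may hold one dose or two, and neither the sampling plan nor the analysis can tell which. In serum the shift is large: about 4.2-fold, with percent R from about 70% to 55%, if the dose comes just before the draw. In fluid it runs from negligible to substantial (1.03 to 3.4-fold; 0.3 to about 12 points of percent R). The direction is certain under the model and the size is not.

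These figures rest on the section 1.5.2 half-lives and volume, the equal split and volumes assumed, and an assumed equilibration half-life of 0.25 to 6.5 h. The documents do not support saying that all 6 h samples are compromised, nor that the pre-versus-post comparison fails. The point is worth acting on because the remedy is cheap and the samples cannot be retaken.

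**What to change.** In sections 10.2 and 10.3:

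- Tie the 1, 6 and 24 h times to the initial dose, as is already done for 48 h.
- Schedule the 6 h blood and fluid draw before any elective dose due then, without delaying or changing care.
- Record the clock time of every draw and every dose.

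In section 11.2.1, state that a 6 h sample drawn after an elective dose is flagged, left out of the single-dose 6 h concentration and percent-R summaries, and reported separately by number of doses received.

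Separately, reconcile section 9.2 with sections 9.0 and 10.2 on whether patients given additional ketorolac stay in the study.

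The cost is a few sentences and some clock times on the case report form, with no extra samples. The downside is that some of the 7-10 complete sets may lose a 6 h value. Draw order does not deal with the larger multi-dose effect at 24 h: after doses at 0, 6, 12 and 18 h, serum total is about 26 times the one-dose value and percent R is 76.1% instead of 96.5%. That needs analysis by number of doses received, which the recorded times would make possible.

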Data will be analyzed as a repeated measure ANOVA followed by Tukey's post hoc analysis in order to evaluate whether there are significant differences between groups (pre-and post-ketorolac treatment). We plan to group both dose groups together as we anticipate similar drug measures based on known prior serum pharmacokinetic studies. If we find a large discrepancy in peritoneal ketorolac concentrations between the 15mg and 30mg treated group, we may amend the protocol to increase sample size to evaluate the groups independently. The analysis of demographic characteristics (age and ethnicity) and clinical characteristics, including histologic tumor type, and stage of disease will be descriptive. For the peritoneal distribution study, seven patients should be sufficient for statistically meaningful results based on a study of similar design to measure concentration of doxorubicin in ovarian ascites following IV administration (45).

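### Elective 6-hourly re-dosing is allowed but the 24 h analysis does not separate regimens, and the plan does not say whether re-dosing may precede the 24 h sample

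*Combined protocol and SAP*

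**What the plan says.** Section 9.0 gives every patient one dose: "The single dose will be considered the study dose for which all consenting eligible patients will receive". For patients with a pain response and "no contraindications to multi-dose (every 6 hours over 24 hours), additional doses will be given per physician discretion based on clinical indication". It keeps these patients in sampling: "Patients receiving 24 hour dosing will be eligible for sample time points after 24 hour dosing".

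Sections 10.2 and 10.3 set peritoneal samples at predose, 1, 6 and 24 hours after ketorolac for all patients, and "an additional 48 hour sample (after the initial dose) will be done in patients having elective multiple ketorolac dosing". The footnote to the sampling table in 10.3 marks only the 48-hour row as an "elective time-point for patients receiving clinically indicated multiple dosing of ketorolac".

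Sections 11.2.1 and 11.2.2 plan a repeated-measures ANOVA with Tukey tests, comparing pre- with post-ketorolac values. On dose level the plan is explicit: "We plan to group both dose groups together as we anticipate similar drug measures". There is a contingency, opening "If we find a large discrepancy in peritoneal ketorolac concentrations between the 15mg and 30mg treated group", under which the sample size may be increased. On single versus multiple dosing these sections say nothing.

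Section 9.2 lists a need for more ketorolac during the collection period among the reasons an investigator may discontinue a patient.

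**The concern.** Peritoneal concentration of R- and S-ketorolac and the percent racemic mixture are the primary objective (2.1). A 24-hour value is interpretable only if one knows how many doses preceded it and how long ago the last was given. If 6-hourly dosing starts before the 24-hour draw, some samples are taken 24 hours after the only dose. Others are taken 6 hours after a fourth dose, or 18 hours after a second. The planned ANOVA treats them as one level.

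With 7 to 10 complete sets, one or two re-dosed patients could then move the 24-hour mean, its variance, the R:S ratio and every Tukey contrast involving 24 hours. Two related gaps follow:

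- The second dose would fall due at the same time as the 6-hour draw, and no order is given.
- The 48-hour level exists only for re-dosed patients, and its place in the ANOVA is not stated.

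**Working it through.** **The plan's own figures.** Section 11.2.1 expects a 60% loss from 60 recruits: 60 × (1 − 0.60) = 24, against the stated 25. It then loses 15 to 18: 25 − 18 = 7 and 25 − 15 = 10. The target of 7 to 10 sets reproduces. The plan gives no alpha, power, SD or re-dosing frequency, so the sizes below come from a model.

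**Inputs.** From 1.5.2: plasma half-lives of 5 h (SD 1.7) for R and 2.5 h (SD 0.4) for S, and a volume of about 13 L. From 8.1 and 9.0: a 6-hour dosing interval. From 10.3.1: a lowest standard of 0.025 mcg/mL. Assumptions: first-order decay, equal starting R and S, and a full course at 0, 6, 12 and 18 h. Section 1.5.2 calls the intraperitoneal distribution unknown, so two slower cases are also shown: a 12 h half-life, and a 12 h equilibration delay (both assumed).

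**R-ketorolac at 24 h.** With half-life h and n doses, C(24) = C0 × Σ 2^(−(24−6k)/h), k = 0 to n−1. At h = 5 the terms are 0.0359, 0.0825, 0.1895 and 0.4353.

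- Two doses against one: (0.0359 + 0.0825)/0.0359 = 3.3.
- Four doses against one: 0.743/0.0359 = 20.7.

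For the delay, dP/dt = kp(C − P). With a 5 h plasma half-life and a 12 h equilibration half-time, a single dose gives P(t) proportional to 2^(−t/12) − 2^(−t/5). This is 0.214, 0.271, 0.311 and 0.272 at 24, 18, 12 and 6 h. The ratios are (0.214 + 0.271)/0.214 = 2.3 and 1.068/0.214 = 5.0.

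| Assumption | Two doses vs one | Four doses vs one |
|---|---|---|
| Half-life 5 h, no delay | 3.3 | 20.7 |
| Half-life 12 h, no delay | 2.4 | 7.2 |
| Half-life 5 h, 12 h delay | 2.3 | 5.0 |

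Moving the plasma half-life by one SD without delay gives 2.9 and 12.8 (6.7 h) or 4.5 and 60.8 (3.3 h). Every ratio exceeds the nominal twofold difference between 15 and 30 mg, for which the plan does have a contingency.

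**Effect on a pooled mean.** If one of seven patients had four doses (assumed), the pooled 24 h mean of R is (6 + 20.7)/7 = 3.8 times the single-dose value at 5 h, or (6 + 5.0)/7 = 1.6 times with the delay.

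**Percent R.** At plasma half-lives the single-dose S term is 2^(−24/2.5) = 0.00129, and the four-dose sum is 0.233. Percent R is 0.0359/(0.0359 + 0.00129) = 96.5% after one dose and 0.743/(0.743 + 0.233) = 76.1% after four. With C0 = 30/13/2 = 1.154 mcg/mL, however, single-dose S is 1.154 × 0.00129 = 0.0015 mcg/mL. Starting instead from half the 4.65 mcg/mL Cmax, it is 0.0030. Both lie well below 0.025, so 96.5% could not be measured. Re-dosed S, 1.154 × 0.233 = 0.27, could be.

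Slower kinetics change this. At 12 h (R) and 6 h (S), single-dose S is 1.154 × 2^(−4) = 0.072 mcg/mL, which is measurable, and percent R goes from 80.0% to 65.9%. With the 12 h delay it goes from 70.0% to 64.8%. With equal half-lives it does not move.

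**The 6 h sample.** Drawn just after instead of just before a second dose, R would read at most (0.435 + 1)/0.435 = 3.3 times higher at 5 h, or 2.4 times at 12 h. At plasma half-lives percent R would be 1.435/(1.435 + 1.189) = 54.7% instead of 0.435/(0.435 + 0.189) = 69.7%.

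**The case against.** The strongest reply is that the mixing depends on a reading. The words tying a sample to the initial dose attach only to the 48-hour sample; the other times are simply after ketorolac. Section 9.0 gives an interval and a duration for re-dosing but no start. A course begun after the 24-hour draw would fit the discontinuation reason in 9.2 and the reference in 9.0 to time points after 24-hour dosing. It would also put the 48-hour sample near the end of the course, whereas dosing at 0 to 18 h puts it 30 hours after the last dose. On that sequence nothing is mixed. This stands as a possible reading, but it is stated nowhere. An additional 48-hour sample for re-dosed patients is more naturally read as coming after a 24-hour sample they also gave while on the course.

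Second, silence is not a pooling rule. A reader might infer that the plan intends to pool regimens; it says so only for the 15 and 30 mg doses. Dispensing records are source documents (12.1), so the 24-hour data could be split afterwards. That is true, but the planned analysis does not call for it.

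Third, a reader might infer that a 6-hour sample taken after a second dose spoils the data beyond repair. With recorded times it could be flagged or excluded. What is lost is that patient's single-dose 6-hour value, and no text suggests drawing after re-dosing.

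Fourth, this is a feasibility pilot with a descriptive aim, and 11.2.2 already plans a trend analysis on measured R-ketorolac. That partly accounts for exposure in the cell assays; the pre/post ANOVA does not.

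**Conclusion.** The concern holds as a conditional one. The plan leaves open whether elective re-dosing may precede the 24-hour sample, 9.2 conflicts with 9.0 and 10.2, and the analysis has no term or rule for regimen. If re-dosing does start earlier, the 24-hour concentration and R:S ratio combine different exposures under one label. R would be about 2 to 3 times higher with one extra dose and about 5 to 21 times higher after four. These figures rest on plasma half-lives or assumed slower kinetics, and the effect is nil if nobody is re-dosed before 24 hours.

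Two stronger readings are not supported. The documents do not establish that the 24-hour result will be distorted by some 20-fold or more: that needs a full course before the draw and near-instant equilibration, and no re-dosing frequency is given. Nor can a fall in percent R from 96.5% to 76.1% be claimed as an observable shift, because at those half-lives single-dose S is below the lowest standard. The sounder statement is that percent R at 24 hours after one dose may not be quantifiable.

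Predose and 1-hour data, and whether drug reaches the peritoneum at all, are not affected. This is worth fixing because the remedy is cheap, not because the trial's main question is in danger.

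**What to change.** - State in 9.0 and 9.2 whether elective re-dosing may begin before the 24-hour sample, and whether it is a reason to stop sampling.
- Draw the 6-hour sample before any second dose.
- Record the number of doses and the time since the last dose for each sample.
- Report 24-hour concentration, R:S ratio (flagging values below 0.025 mcg/mL) and cell-assay results by regimen.
- Limit 24-hour pre/post contrasts to patients not yet re-dosed, or show them by regimen.
- Keep the 48-hour data descriptive and outside the Tukey contrasts.

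The cost is a few sentences, a fixed draw order and a case report form field for dose times, which dispensing records can support. No patients or procedures are added. The real downside is smaller 24-hour subgroups among 7 to 10 patients, so that time point becomes largely descriptive.
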